### 3.5 Dose Modifications

**NOTE:** Patients who interrupt trametinib and dabrafenib for > 2 weeks will be removed from this subprotocol, unless the interruption was for reduction in LVEF, visual changes or RPED with subsequent recovery as described in corresponding tables below.

All toxicity grades below are described using the NCI Common Terminology Criteria for Adverse Events (CTCAE) version 4.0.

All appropriate treatment areas should have access to a copy of the CTCAE version 4.0. A copy of the CTCAE version 4.0 can be downloaded from the CTEP website (<https://dctd.cancer.gov/research/ctep-trials/sites/adverse-events>).

The table below outlines the dose levels to be used for any necessary dabrafenib and trametinib dose modifications in studies which include the combination:

Dose Level	Dabrafenib Dose/Schedule
0	150 mg BID
-1	100 mg BID
-2	75 mg BID
-3	50 mg BID

Dose Level	Trametinib Dose/Schedule
0	2 mg QD
-1	1.5 mg QD
-2	1.0 mg QD

#### **Dabrafenib and Trametinib Dose Modification Guidelines**

If an AE resolves to grade 1 or baseline at the reduced dose level, and no additional toxicities are seen after 4 weeks of study treatment at the reduced dose, the dose may be increased to the previous dose level. A dose reduction below 50 mg BID for dabrafenib is not allowed. For dabrafenib-trametinib combination, dose below 1 mg once daily for trametinib is not allowed; however, if dabrafenib will be permanently discontinued for dabrafenib-related toxicities, the patients will be allowed to continue trametinib. Conversely, if trametinib is permanently discontinued for trametinib-related toxicities, patients will be allowed to continue dabrafenib.

The dose modifications may involve one or both agents, and should be based on the nature, severity and attributions of the AEs. General guidelines are provided in Tables below, with details stipulated in subsequent sections. The CTEP drug monitors should be consulted if there are questions about the attribution of AEs and how the doses should be modified.

3.5.1 Dabrafenib-Trametinib Dose Modification for Toxicities Not Specified in Subsequent Sections

Dabrafenib-Trametinib Dose Modification for Toxicities Not Specified in Subsequent Sections	
CTCAE Grade	Action and Dose Modification
Grade 1 Grade 2 (tolerable)	
 
Continue study treatment at same dose level (no dose modification).
 
Monitor closely.
 
Provide supportive care according to institutional standards.
 

Grade 2 (intolerable) Grade 3	
 
Interrupt study treatment.
 
Monitor closely.
 
Provide supportive care according to institutional standards.
 
When toxicity resolves to grade 1 or baseline, restart study treatment reduced by one dose level.
 
If the grade 2 (intolerable) or grade 3 toxicity recurs, interrupt study treatment.
 
When toxicity resolves to grade 1 or baseline, restart study treatment reduced by another dose level.
 

Grade 4	
 
Permanently discontinue, or interrupt, study treatment.
 
Monitor closely.
 
Provide supportive care according to institutional standards.
 
If study treatment was interrupted, restart study treatment reduced by one dose level once toxicity resolves to grade 1 or baseline.
 

* If the AEs are thought to be due to one of the two agents, resumption of the other agents may be considered if the first agent is discontinued due to toxicities and treatment interruption is < 14 days. The subprotocol Study Chair should be consulted for resumption of single agent.
	

Rev. 8/15

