Serum creatinine increase > 0.5 mg/dL (44 mcmmol/L) ABOVE NORMAL OR > 2 mg/dL (> 177 mcmmol/L)	
 
• Monitor serum creatinine ≥ 2-times per week.
 
• Hospitalization may be necessary if serum creatinine cannot be monitored frequently.
 
• If pyrexia is present, treat pyrexia per guidelines.
 
• Consult nephrologist if clinically indicated.
 
• Perform renal biopsy if clinically indicated, for example:               
 
– Renal insufficiency persists despite volume repletion.
 
– Patient has new rash or signs of hypersensitivity (such as elevated eosinophil count).
 
 
 
	
 
• Interrupt study treatment for up to 2 weeks until serum creatinine recovers to baseline.
 
• Restart study treatment.b
 

a NSAIDs can induce renal insufficiency, especially in patients with dehydration; encourage oral fluids or consider IV fluids as clinically indicated. See guidelines for pyrexia Section 3.5.2 . b Investigator may restart at either the same or a reduced dose level. Escalation of study treatment to previous dose level is allowed if another episode of renal insufficiency does not occur after 4 weeks of dose reduction. Consultation with the subprotocol Study Chair is required before restarting study treatment if there is evidence of thrombotic microangiopathy.		

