
Criteria for discontinuing study drug: When any of the liver stopping criteria below is met, discontinue trametinib and dabrafenib
 
 
ALT <math>\geq</math> 3xULN and bilirubin <math>\geq</math> 2x ULN or <math>></math> 35% direct bilirubin
 
ALT <math>\geq</math> 3xULN and INR <math>></math>1.5, if INR measured (INR threshold does not apply if subject is on anticoagulant)
 
ALT <math>\geq</math> 5x ULN
 
ALT <math>\geq</math> 3x ULN persists for <math>\geq</math>4 weeks. However, if ALT was elevated 3-5x at baseline due to liver mets, then this criteria should not be used for treatment discontinuation UNLESS the ALT improves to <math><</math> 3x ULN and then subsequently rises
 
ALT <math>\geq</math> 3x ULN and cannot be monitored weekly for 4 weeks. However, if ALT was elevated 3-5x at baseline due to liver mets, then this criteria should not be used for treatment discontinuation UNLESS the ALT improves to <math><</math> 3x ULN and then subsequently rises.
 
ALT <math>\geq</math> 3x ULN associated with symptoms (new or worsening) believed to be related to liver injury or hypersensitivity
 
	
 
Immediately discontinue study treatment.
 
Do not restart/rechallenge unless approved by the subprotocol Study Chair.
 
Report as SAE if: 1) CTEP-AERS reporting criteria are met, or 2) patients meet criteria 1-2.
 
Perform liver event ASSESSMENT AND WORKUP (see below).
 
Monitor the subject until liver chemistries resolve, stabilize, or return to baseline (see MONITORING below).
 
 
If applicable, provide details on required follow up assessments (e.g., follow up for overall survival or disease recurrence or progression).
 
MONITORING: In patients stopping for criteria 1-2 (with abnormal TB and INR, indicating potentially more significant liver toxicities):
 
 
Repeat liver chemistries (ALT, AST, ALK, bilirubin) and perform liver event follow-up assessments within 24 hours.
 
Monitor subjects twice weekly until LFT return to normal/baseline or stabilize.
 
A specialist or hepatology consultation is recommended.
 
 
In patients stopping for criteria 2-6:
 
 
Repeat LFT and perform liver event follow up assessments within 24-72 hours
 
Monitor subjects weekly until LFTs return to normal/baseline or stabilize.
 
 
ASSESSMENT and WORKUP:
 
 
Viral hepatitis serology.
 
Serum CPK and LDH.
 
Fractionate bilirubin, if total bilirubin <math>\geq</math> 2x ULN.
 
CBC with differential to assess eosinophilia.
 
Record clinical symptoms of liver injury, or hypersensitivity on AE CRF.
 
Record concomitant medications (including acetaminophen, herbal remedies, other over the counter medications).
 
Record alcohol use.
 
 
Additional work up for patient stopping for criteria 1-2 (with abnormal TB and INR, indicating potentially more significant liver toxicities):
 
 
Anti-nuclear antibody, anti-smooth muscle antibody, Type 1 anti-liver kidney microsomal antibodies, and quantitative total immunoglobulin G (IgG or gamma globulins).
 
Serum acetaminophen adduct HPLC assay (in subjects with likely acetaminophen use in the preceding).
 
If there is underlying chronic hepatitis B (e.g. positive hepatitis B surface antigen): quantitative hepatitis B DNA and hepatitis delta antibody.
 
Liver imaging (ultrasound, MRI, CT) and /or liver biopsy.
 

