
Rev. 8/15

Footnotes:

1. Serum bilirubin fractionation should be performed if testing is available. If serum bilirubin fractionation testing is unavailable, record presence of detectable urinary bilirubin on dipstick, which indicates direct bilirubin elevations and suggesting liver injury.
2. All events of ALT  $\geq$  3xULN and bilirubin  $\geq$  2xULN (> 35% direct bilirubin) or ALT  $\geq$  3x ULN and INR > 1.5 (if INR measured) may indicate severe liver injury (possible "Hy's Law"). INR measurement is not required, and the threshold value stated will not apply to subjects receiving anticoagulants.
3. New or worsening symptoms believed to be related to liver injury (such as fatigue, nausea, vomiting, right upper quadrant pain or tenderness, or jaundice) or believed to be related to hypersensitivity (such as fever, rash or eosinophilia)
4. Includes: Hepatitis A IgM antibody; Hepatitis B surface antigen and Hepatitis B Core Antibody (IgM); Hepatitis C RNA; Cytomegalovirus IgM antibody; Epstein-Barr viral capsid antigen IgM antibody (or if unavailable, obtain heterophile antibody or monospot testing); Hepatitis E IgM antibody
5. If hepatitis delta antibody assay cannot be performed, it can be replaced with a PCR of hepatitis D RNA virus (where needed) (Le Gal *et al.*, 2005).

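### Section 3.5 has no rule for drug hypersensitivity, DRESS or Stevens-Johnson syndrome, so sections 3.5.1 and 3.5.3 restart treatment after a severe reaction without Study Chair approval

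*Protocol*

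**What the plan says.** Section 3.5.1 is the fallback table for toxicities without a section of their own. For intolerable grade 2 or grade 3 it interrupts treatment and then directs: "When toxicity resolves to grade 1 or baseline, restart study treatment", one dose level lower. If the toxicity recurs, the instruction after recovery is "restart study treatment reduced by another dose level". For grade 4 it offers two options, "Permanently discontinue, or interrupt, study treatment", and continues "If study treatment was interrupted, restart study treatment" one level lower once the toxicity has resolved. The only Study Chair step is in the footnote, which concerns carrying on with the other drug after the suspected one has been stopped: "The subprotocol Study Chair should be consulted for resumption of single agent".

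Section 3.5.3 (rash), at grade 3 or higher, interrupts, asks for a dermatologist, restarts both drugs one level lower after recovery, and stops permanently if there is no recovery to grade 2 or below within 14 days.

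Section 3.5.16 (liver chemistry) is stricter. One of its stopping criteria is ALT of at least 3x ULN with symptoms of liver injury or symptoms "believed to be related to hypersensitivity (such as fever, rash or eosinophilia"). For any patient who meets a stopping criterion it says: "Do not restart/rechallenge unless approved by the subprotocol Study Chair".

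**The concern.** These reactions are foreseen. Both adverse-event lists (sections 3.3 and 3.4) contain allergic reaction, DRESS and Stevens-Johnson syndrome, and a note in 3.3 says Stevens-Johnson syndrome has been seen with this combination. Section 1.7 reports one dabrafenib reaction (blisters) that appeared on the day of the first dose and came back on rechallenge; the patient recovered once the drug was stopped. Criterion 2.1.13 keeps out patients with known hypersensitivity, yet a patient who becomes hypersensitive on study is, under the written tables, given the suspected drug again.

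At stake is avoidable re-exposure after a severe allergic reaction, possibly more than once, with no mandatory outside check before the restart.

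**Working it through.** There is no planned figure to reproduce. The check is a reading of every subsection of 3.5, followed by tracing where a reaction would land.

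**1. Is there a specific rule?** Sections 3.5.2 to 3.5.17 cover pyrexia, rash, PPES, new malignancies, hemorrhage, pancreatitis, hyperglycemia, renal insufficiency, LVEF, hypertension, QTc, diarrhea, visual changes, pneumonitis, liver chemistry and VTE. None is for hypersensitivity, DRESS or Stevens-Johnson syndrome. Within 3.5, hypersensitivity appears as a work-up item for pyrexia (3.5.2), as a reason to consider renal biopsy (3.5.9), and in the liver section (3.5.16).

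**2. Where does a reaction go?**

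| Presentation | Section | Restart after a severe event | Study Chair approval |
|---|---|---|---|
| Fits no specific table, grade 3 | 3.5.1 | Yes, one level lower; a further level lower after recurrence | No |
| Fits no specific table, grade 4 | 3.5.1 | Permitted, as the alternative to a permanent stop | No |
| Handled as rash, grade 3 or higher | 3.5.3 | Yes, both drugs one level lower | No |
| Hypersensitivity symptoms with ALT at least 3x ULN | 3.5.16 | Only if approved | Yes |

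Two patients with the same grade 3 allergic reaction, one just above and one just below 3x ULN for ALT, are thus handled differently. The first is not rechallenged without approval; the second is restarted under 3.5.1 or 3.5.3.

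**3. At what dose is the patient re-exposed under 3.5.1?** From the dose-level tables in 3.5:
- Dabrafenib: 100/150 = 67%, then 75/150 = 50% of the starting dose.
- Trametinib: 1.5/2 = 75%, then 1.0/2 = 50%.

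The general text of 3.5 also allows a return to the previous level after 4 weeks without further toxicity.

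**4. How does the protocol treat restart after other events?** Six of the 16 specific sections send some restart to the Study Chair: 3.5.9, 3.5.10, 3.5.12, 3.5.14, 3.5.15 and 3.5.16. For example, 3.5.9 says: "Consultation with the subprotocol Study Chair is required before restarting study treatment if there is evidence of thrombotic microangiopathy". Sections 3.5.10, 3.5.12 and 3.5.16 ask for approval or agreement; 3.5.9, 3.5.14 and 3.5.15 ask for consultation or discussion. The other 16 - 6 = 10 have no such step. Section 3.5.12 also stops permanently on recurrence, where 3.5.1 restarts.

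**5. Does any general clause close the gap?**
- The opening note of 3.5 removes patients who interrupt both drugs for more than 2 weeks. A reaction that resolves sooner is unaffected.
- The general guidelines in 3.5 base action on the nature, severity and attribution of the event, and point to the CTEP drug monitors if there are questions. This is discretion, not a required stop.
- Section 3.5.3 allows clinical judgment where institutional skin standards differ, and says Study Chair consultation may be needed. It is not made mandatory.
- Section 3.7 ends treatment for unacceptable toxicity, without defining it.

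Each allows a stop or a consultation. None requires one.

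**The case against.** The strongest reply is that the tables are general guidelines and no sensible investigator would rechallenge after a severe allergic reaction. That is likely true in many cases, and the clauses in step 5 support it. It does not change what a site following the table literally would do.

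Several further points stand:
- The reactions described in section 1.7 do not clearly reach 3.5.1. The blister case is ungraded and may belong under rash, since section 3.4 describes dabrafenib allergy as possibly presenting as bullous rash. The trametinib case had fever, visual disturbance and raised liver tests, each of which has its own table. Section 1.7 also calls the etiology of the reported dabrafenib events unclear. A reader might take the rechallenge case as proof that 3.5.1 causes harm; it shows only that recurrence on rechallenge has been reported.
- A reader might infer that 3.5.1 contradicts 3.5.16, or breaks a consistent policy. It does neither. The liver rule has its own ALT threshold, and ten of the 16 specific sections have no Study Chair restart step; grade 3 hemorrhage (3.5.6), for instance, resumes without one.
- Neither adverse-event list gives an expedited-reporting exception for allergic reaction, DRESS or Stevens-Johnson syndrome. Reporting, however, is not approval before restart.
- The benefit now is small. Accrual was to stop on December 31, 2022, and the adverse-event lists are dated January and July 2025, so remaining patients have probably been on treatment for more than two years. The two cases with stated timing began on the day of the first dose and 7 days after starting.

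**Conclusion.** The point holds as a gap in a stated safety rule. For a listed risk of both drugs, the written default after a grade 3 reaction outside the specific tables, or a rash of grade 3 or higher, is a reduced-dose restart without Study Chair approval. After grade 4 under 3.5.1 a restart is permitted, not directed.

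Its size cannot be stated as a rate. A reader might divide the one trametinib case by the 329-subject trametinib population in section 1.7 (1/329 = 0.3%), or take the under-3% column for dabrafenib, and scale to the roughly 80 analyzable patients. The documents do not support this. It is not stated that the case belongs to that population, the 3% is an any-grade ceiling, the trametinib list puts allergic reaction in its up-to-20% column, and none of these counts severe reactions that reach 3.5.1 or 3.5.3.

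The conclusion assumes that the MATCH Master Protocol, which is not at hand, has no overriding hypersensitivity rule; section 3.5 does not refer to it for one. It is worth correcting because the harm could be serious and the change is cheap. With accrual closed, only patients still on treatment can benefit, and their number is not given.

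**What to change.** Add one row to 3.5.1, cross-referenced from 3.5.3:

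- *Drug hypersensitivity of grade 3:* stop the suspected drug or drugs, or both if they cannot be told apart. Then apply the sentence already used in 3.5.16: "Do not restart/rechallenge unless approved by the subprotocol Study Chair".
- *Grade 4 hypersensitivity, DRESS, Stevens-Johnson syndrome, or recurrence on rechallenge:* permanently discontinue the suspected drug or drugs.

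Leave grade 2 handling and the pyrexia dosing in 3.5.2 as they are. Extending the row to intolerable grade 2, or letting it override the pyrexia table, would be a debatable trade-off and is not needed to close this gap.

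The cost is one row and one cross-reference in the next addendum, with no new assessment. The downside is that an occasional patient waits for approval, which must come within 2 weeks if both drugs are held, or loses a drug that might have been tolerated.

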3.5.2 Dabrafenib-Trametinib Dose Modification for Pyrexia

- Pyrexia is defined as a body temperature equal to or above 38.5° Celsius or 101.3° Fahrenheit
- Pyrexia is an adverse event associated with dabrafenib and is increased in frequency and severity in subjects receiving dabrafenib in combination with trametinib. In a minority of cases, pyrexia was accompanied by symptoms such as severe chills/rigors, dehydration, hypotension, dizziness or weakness and required hospitalization.
- Subjects should be instructed on the importance of immediately reporting febrile episodes. In the event of a fever, the subject should be instructed to take anti-pyretics (e.g. ibuprofen or acetaminophen/paracetamol) as appropriate to control fever. The use of oral corticosteroids should be considered in those instances in which anti-pyretics are insufficient. Monitor serum creatinine and other evidence of renal function during and following severe events of pyrexia

Dabrafenib-Trametinib dose Modification and Management Guidelines for Pyrexia		
Event	Management Guideline	Dose Modification

Work up:
 
 
Clinical evaluation for infection and hypersensitivity, especially if pyrexia is complicated by rigors, severe chills, dehydration, etc.
 
Laboratory work-up (should include full-blood-count, electrolytes, creatinine, BUN, CRP, liver-function tests, blood and urine culture).
 
 
Management:
 
 
Anti-pyretic treatment should be started immediately at the first occurrence. Anti-pyretic treatment may include acetaminophen (paracetamol), ibuprofen, or suitable anti-pyretic medication per institutional standards.
 
Oral hydration is encouraged in subjects without evidence of dehydration. Intravenous hydration is recommended if pyrexia is complicated by dehydration/hypotension.
 
In subject experiencing pyrexia complicated by rigors, severe chills, etc., which cannot be controlled with anti-pyretic medication, oral corticosteroids should be started.
 
Prophylactic anti-pyretic treatment is recommended after the 2nd event, or after the 1st event if complicated by rigors or severe chills. Prophylactic anti-pyretics may be discontinued after three days in absence of pyrexia
 
		
1st Event:	
 
Clinical evaluation for infection and hypersensitivity
 
Laboratory work-up
 
Hydration as required
 
Administer anti-pyretic treatment if clinically indicated and continue prophylactic treatment
 
	
 
Interrupt dabrafenib.
 
Continue trametinib.
 
Upon recovery to baseline, restart dabrafenib at the same dose level. If fever was associated with dehydration or hypotension, reduce dabrafenib by one dose level.
 

2nd Event	
 
Clinical evaluation for infection and hypersensitivity
 
Laboratory work-up
 
Hydration as required
 
Within 3 days of onset of pyrexia: 
 
Optimize anti-pyretic therapy.
 
Consider oral corticosteroids (i.e., prednisone 10 mg) for at least 5 days or as clinically indicated.
 
 
 
	
 
Interrupt dabrafenib.
 
Continue trametinib
 
Upon recovery to baseline, restart dabrafenib at the same dose level. If fever was associated with dehydration or hypotension, reduce dabrafenib by one dose level.
 

Subsequent Events:	
 
Clinical evaluation for infection and hypersensitivity
 
Laboratory work-up
 
Hydration as required
 
Blood sample for cytokine analysis
 
Within 3 days of onset of pyrexia: 
 
Optimize oral corticosteroid dose as clinically indicated for recalcitrant pyrexia.
 
If corticosteroids have been tapered and pyrexia recurs, restart steroids.
 
If corticosteroids cannot be tapered, consult the subprotocol Study Chair.
 
 
 
	
 
Interrupt dabrafenib.
 
Continue trametinib.
 
Once pyrexia resolves to baseline, restart dabrafenib reduced by one dose level.
 
If dabrafenib must be reduced to < 50 mg BID, permanently discontinue dabrafenib.
 

Dabrafenib should be reduced by one dose level after three episodes of pyrexia which cannot be managed by best supportive care and increasing doses of oral steroids. Escalation of dabrafenib is allowed if no episode of pyrexia is observed in the 4 weeks subsequent to dose reduction.
		

Rev. 12/16

Rev. 8/15

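### In the pyrexia table, the row for third and later events and the footer give different triggers for reducing dabrafenib, and the antipyretic instructions do not match either

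*Protocol*

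**What the plan says.** The table in Protocol section 3.5.2 has a header block on work-up and management, three event rows and a footer.

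**Dose action.** For the 1st and 2nd events dabrafenib is interrupted, then: "Upon recovery to baseline, restart dabrafenib at the same dose level. If fever was associated with dehydration or hypotension", in which case it comes back one level lower. For subsequent events, meaning the third onward, it is again interrupted, then "Once pyrexia resolves to baseline, restart dabrafenib" at one level lower. That row does not ask how well the episode was controlled. It ends in permanent discontinuation if the dose would have to go under 50 mg BID. The footer then states: "Dabrafenib should be reduced by one dose level after three episodes of pyrexia which cannot be managed by best supportive care", and the condition goes on to include oral steroids at increasing doses. The footer also permits re-escalation after 4 weeks without pyrexia following a reduction.

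**Antipyretics.** The header block says "Anti-pyretic treatment should be started immediately at the first occurrence". It recommends prophylaxis after the 2nd event, or after the 1st "event if complicated by rigors or severe chills". The 1st Event row says "Administer anti-pyretic treatment if clinically indicated and continue prophylactic treatment".

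**The concern.** The same table gives two triggers for the same one-level reduction. One counts episodes. The other also asks whether supportive care and steroids failed. Two sites treating the same patient history could each follow the table and reach different dabrafenib doses.

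This matters because section 1.6 lists pyrexia among the commonest reasons for dose reduction and interruption on the combination, and section 1.7 gives it the highest all-grade rate in the table for the 150/2 arm. In a single-arm trial that estimates a response rate, avoidable site-to-site differences in dosing make exposure and safety data harder to interpret.

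The antipyretic wording is a lesser matter: it affects supportive care and has no direct dose consequence.

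**Working it through.** There is no plan figure to reproduce. The check sets the lines of the table against each other, then follows the dose levels in section 3.5.

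**1. Row against footer at the third episode**

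| History | Subsequent Events row | Footer condition: "after three episodes of pyrexia which cannot be managed by best supportive care and increasing doses of oral steroids" | Agree? |
|---|---|---|---|
| Third episode, all three uncontrolled | Reduce one level | Met | Yes |
| Third episode, controlled | Reduce one level | Not met | No |

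For a mixed history, the footer does not say whether all three episodes must have been unmanageable. It is also silent on the dehydration or hypotension reductions that the first two rows allow.

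**2. Can the footer be read so that it does not conflict?** It does not contain the word *only*, so it could be a sufficient condition. But anyone with three unmanageable episodes has reached the Subsequent Events row and is already reduced there. On that reading the footer's condition has no effect. It does some work only if it restricts the reduction, and then it conflicts with the row.

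**3. How the difference can grow.** Section 3.5 gives dabrafenib levels of 150, 100, 75 and 50 mg BID. Assume a start at 150 mg BID, no reduction at events 1 or 2, every episode controlled, and no re-escalation.

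| Event | Dose on restart under the row | Footer condition met? |
|---|---|---|
| 3 | 100 mg BID | No |
| 4 | 75 mg BID | No |
| 5 | 50 mg BID | No |
| 6 | Next step is below 50 mg BID, so permanent discontinuation | No |

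Under the footer alone, the trigger is never met in this history. Re-escalation after 4 fever-free weeks would narrow the gap, but is not open to a patient whose episodes recur within 4 weeks.

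**4. Antipyretics at an uncomplicated first event**

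| Action | Header block | 1st Event row |
|---|---|---|
| Treatment | At once, no condition | If clinically indicated |
| Prophylaxis | Not yet recommended | Continue it |

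Under the header block this patient would have no prophylaxis to continue.

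**5. Number of patients.** The 71% in section 1.7 (150/2 arm, n=55) applied to the accrual goal gives 0.71 × 85 = 60.35, about 60 patients with any pyrexia. Those with a controlled third episode are an unknown part of that group. If the earlier study's rate held here, the number lies anywhere from 0 to about 60, so 60 is a ceiling and not an estimate.

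**The case against.** The strongest reply has four parts.

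- **The wording is advisory.** The table is headed as guidelines, the footer says *should*, and section 3.5 bases modifications on the nature, severity and attribution of the event, with questions going to the CTEP drug monitors. This stands in part. It is too strong to say the footer requires a reduction or forbids one otherwise, but a route for asking questions does not make the two lines agree.
- **The two groups overlap.** By a third event, prophylaxis is recommended, antipyretics should have been optimized and steroids considered, and the row itself speaks of recalcitrant fever. Many such patients may meet the footer as well. This stands, and it confines the conflict mainly to a third or later episode that is controlled.
- **The dose effect is bounded.** The footer allows re-escalation, and section 1.7 reports that over 80% of subjects who reduced dabrafenib for adverse events could be re-escalated. This stands as a limit on the consequence, though that figure is not specific to repeated pyrexia.
- **The antipyretic mismatch is loose wording.** Text above the table speaks of antipyretics as appropriate, which fits the row, and continued prophylaxis makes sense after a complicated first event. The uncomplicated first event is still described in two ways.

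A reader might also infer that about 60 of 85 patients are affected, or that the trial's activity result depends on which line a site follows. The documents support neither. The 60 counts any pyrexia at another study's rate. The statement in section 1.7 that about half of pyrexia-related events led to interruption or reduction does not measure this conflict, since all three rows here interrupt dabrafenib and only the restart dose differs. The response rates of 50% at 150 mg BID and 17% at 50 mg BID in section 1.5 come from dabrafenib monotherapy in melanoma and say nothing about this combination in these tumors.

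**Conclusion.** The inconsistency is real and lies within one table. For a controlled third or later episode, the Subsequent Events row reduces dabrafenib while the footer's condition is not met. This rests on reading the footer as a restriction, which is the only reading that gives its condition any effect.

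For one patient, the gap can run from no footer-triggered reduction to permanent discontinuation at a sixth event, under the assumptions stated with the dose sequence. Across the trial its size is unknown. The antipyretic mismatch is genuine but secondary. This is a flaw in a dosing instruction that should be corrected; it is not shown to alter the response rate, its confidence interval or any other planned analysis.

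**What to change.** The sponsor should reconcile the Subsequent Events row with the footer so that one stated trigger governs the one-level reduction, and say how it relates to reductions already made for dehydration or hypotension. The header block and the 1st Event row should likewise be reconciled, so that one statement governs the start of antipyretic treatment and one governs prophylaxis. Which rule applies is a clinical decision for the sponsor.

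The cost is a change of wording in the section 3.5.2 table. Section 1.9 set the end of accrual at December 31, 2022, and the adverse event lists in sections 3.3 and 3.4 are dated 2025, so new wording would reach only patients still on treatment; the protocol does not say how many there are. For patients already treated, a note of which line was followed would help in interpreting the dosing data.
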